### 7.2. Demographic and Other Baseline Characteristics

Patient demographics and baseline characteristics will be examined to assess the comparability of the treatment groups. BMI will be computed as:

$$\text{BMI (kg/m}^2\text{)} = \text{Weight at baseline (kg)} / [\text{Height at screening (m)}]^2$$

In addition, normal age and sex-based z-scores and percentiles for BMI will be determined using the WHO growth charts. Age and sex-based BMI categories includes: Underweight (< 5 percentile), Normal ( $\geq 5$  - < 85 percentile), Overweight ( $\geq 85$  - < 95 percentile), Obese ( $\geq 95$  percentile).

The continuous variables of patient age, weight, height, body mass index (BMI), BMI World Health Organization (WHO) adjusted z-scores and percentile, will be summarized using descriptive statistics. The categorical variables of patient sex, race, ethnicity, and BMI categories will be summarized using descriptive statistics for each category. Missing categories will be presented if necessary. For randomized patients, age at baseline will be used.

The continuous variables of time since Tourette syndrome diagnosis in years and baseline TTS of the YGTSS will be summarized using descriptive statistics. The categorical variables of age group at baseline (6 to 11 years, 12 to 16 years), use of a strong CYP2D6 inhibitor (Yes/No), CYP2D6 genotype (Poor CYP2D6 metabolizer/ Non-poor CYP2D6 metabolizer), and CYP2D6 impairment status (Impaired/Not impaired) will be summarized using descriptive statistics for each category.

Strong CYP2D6 inhibitor status is determined by classifying patients as taking versus not taking a strong CYP2D6 inhibitor (i.e. paroxetine, fluoxetine, or bupropion), collected at screening from site. Impaired CYP2D6 function is defined as use of a strong CYP2D6 inhibitor at baseline or a poor CYP2D6 metabolizer. Both CYP2D6 genotype and impairment status will be blinded during the study.

This document is confidential.

Summaries for demographics and baseline characteristics will also be presented for the ITT, safety, mITT and PP analysis sets.

### **7.3. Medical History and Concomitant Diseases**

Significant medical and psychiatric history, including dates of diagnoses and procedures and whether the condition is ongoing, if applicable, will be collected. Each condition will be recorded as a verbatim term, date of onset, date resolved, and a checkbox that indicates ongoing conditions. Significant surgical and medical history will be coded using the Medical Dictionary for Regulatory Activities (MedDRA) Version 20.1.

Medical and surgical history will be summarized for the safety analysis set by treatment group, system organ class (SOC), and MedDRA preferred term (PT). Patient data will be listed.

### **7.4. Medication**

Any prior therapy, medication, or procedure a patient has had within 3 months before study drug administration will be recorded on the case report form (CRF). Medications will be coded according to the WHO Drug Version: June 2017. Preferred drug name, Anatomical/ Therapeutic/ Chemical (ATC) class will be reported for inclusion in the database.

Medication summaries based on ATC level 3 and the preferred drug names will be produced for the safety analysis set. The summaries will present, by treatment group, the frequency and percentage of patients who used any medication in an ATC class, or any medication based on a single preferred drug name. Medication summaries will be sorted by descending total frequency of ATC class and by PT within ATC class. Patients will be counted only once for each medication class and each preferred drug name.

#### **7.4.1. Prior Medication**

Prior medications and therapies will include all medications and therapies stopped before the first day of study drug administration. Prior medication will be summarized by the ATC level 3 and preferred name. Prior medication will be summarized. The same summary will be repeated for prior antidepressant and ADHD medication use. These medications are identified by the ATC codes of:

ADHD medications:

N-NERVOUS SYSTEM

N06-PSYCHOANALEPTICS

N06B-PSYCHOSTIMULANTS, AGENTS USED FOR ADHD AND NOOTROPICS

N06BA-Centrally acting sympathomimetics

N06BC-Xanthine derivatives

N06BX-Other psychostimulants and nootropics.

Antidepressant:

N-NERVOUS SYSTEM

N06-PSYCHOANALEPTICS

N06A-ANTIDEPRESSANTS

N06AA-Non-selective monoamine reuptake inhibitors

N06AB-Selective serotonin reuptake inhibitors

N06AF-Monoamine oxidase inhibitors, non-selective

N06AG-Monoamine oxidase A inhibitors

N06AX-Other antidepressants.

This document is confidential.

**Statistical Analysis Plan for Interventional Studies**

Sponsor: Teva Branded Pharmaceutical Products R&D, Inc./Nuvelution TS Pharma, INC.;  
Protocol No.: TV50717-CNS-30060

---

7.4.2. Other Therapies

Prior non-pharmacological treatment will be collected in CRF. Type of treatment/procedure and indication will be listed.

Prior treatment given for TS will be summarized. The table will include number of patients with previous treatment given for TS, total duration of treatment, and best response to treatment. For an ongoing treatment, date of informed consent will be used to compute duration. If the start date is partial with year and month, 1st will be imputed. If the start date has only year, Jan, 1st will be imputed. If the end date is partial, the latest possible date on or before informed consent date will be imputed. If there are multiple prior treatments, the duration will be computed as the sum of all non-overlapping treatments. For overlapping treatments, the duration will be from the earliest treatment start date to the latest treatment end date.

This document is confidential.

## **8. Efficacy**

The mITT analysis set will be used for all efficacy analyses, unless otherwise noted. Analyses and summaries will be presented by treatment group.

Week 9 efficacy data will be summarized but will not be included in any statistical analyses.

### **8.1. Efficacy Assessment and Time Points**

#### **8.1.1. Yale Global Tic Severity Scale (YGTSS)**

The YGTSS rating scale is a semi-structured clinician rating instrument that provides an evaluation of the number, frequency, intensity, complexity, and interference of motor and phonic tics (Leckman et al 1989). The YGTSS is composed of 11 items: 5 items for motor tic severity, 5 items for vocal tic severity, and 1 item for impairment. Each item for motor tic severity and vocal is rated on a 6-point scale (0 for none to 5 to severe). The MTSS is the sum of the 5 items for motor tic severity and the VTSS is the sum of the 5 items for vocal tic severity. The TTS is the sum of the MTSS and the VTSS. The impairment score ranges from 0 (none) to 50 (severe). The GSS is the sum of the TTS and the impairment score.

YGTSS is administered at screening; baseline; and weeks 2, 4, 8, and 9.

For YGTSS, if a response to 1 item is missing within the MTSS or VTSS subscale, the missing response will be replaced with the average of the remaining responses within the subscale; if responses to 2 or more items within a subscale are missing, the missing responses will not be replaced and the subscale score will be set to missing; if at least 1 subscale is missing then the TTS will be set to missing. If the TTS or impairment score are missing, then the GSS will be set to missing.

#### **8.1.2. Tourette Syndrome-Clinical Global Impression (TS-CGI)**

The TS-CGI is administered at baseline and at weeks 2, 4, 8, and 9. The TS-CGI scale is a 7-point Likert scale that allows the clinician to use all available information to assess the impact of tics on the patient's quality of life. The TS-CGI is rated as follows: 1 (normal), 2 (borderline), 3 (mild), 4 (moderate), 5 (marked), 6 (severe), and 7 (extreme).

#### **8.1.3. Tourette Syndrome-Patient Global Impression of Impact (TS-PGII)**

The TS-PGII is administered at baseline and weeks 2, 4, 8, and 9. Input from the caregiver/adult is permitted.

The TS-PGII is a single-item questionnaire that asks the patient to assess the degree of impact due to current tics. The TS-PGII uses a 5-point scale, ranging from not at all (1) to very much (5), to assess overall response to therapy. In general, patient-rated global measures of change have face validity and have been shown to correlate with disability for a number of chronic conditions.

#### **8.1.4. Child and Adolescent Gilles de la Tourette Syndrome – Quality of Life (C&A-GTS QOL)**

The C&A-GTS-QOL is administered at baseline, week 4, and week 8. Children 13 years of age and under may be interviewed separately or jointly with the caregiver/adult as appropriate or defined by the scale. For children over 13 years of age, caregiver/adult involvement is strongly encouraged. Questions should be directed to the child, but the caregiver/adult should be encouraged to add relevant information.

**This document is confidential.**

**Statistical Analysis Plan for Interventional Studies**

Sponsor: Teva Branded Pharmaceutical Products R&D, Inc./Nuvelution TS Pharma, INC.;  
Protocol No.: TV50717-CNS-30060

---

The C&A-GTS-QOL is a 27-item questionnaire specific to TS patients that asks the patient to assess the extent to which their quality of life is impacted by their symptoms. The C&A-GTS-QOL contains 6 subscales (cognitive, coprophenomena, psychological, physical, obsessive-compulsive, and ADL) and uses a 5-point Likert scale ranging from no problem to extreme problem. Patients will also be asked how satisfied they feel overall with their life at that moment by using a VAS scale between 0 and 100 (Su et al 2017). Following are the questions assessed in each C&A-GTS-QOL subscale:

- Cognitive (questions 11, 12, 13, 14, 18, 20, 21, 23) (range: 0- 32)
- Psychological (questions 15, 16, 17, 19, 25, 27) (range: 0 – 24)
- Obsessive-compulsive (questions 7, 8, 9, 10) (range: 0 – 16)
- Physical (questions 1, 3, 4) (range: 0 – 12)
- Coprophenomena (questions 5, 6, 22) (range: 0 -12)
- ADL (questions 2, 24, 26) (range: 0-12)

Scores for the six subscales are generated by summing items and, for ease of interpretation, transformation to a range of 0 to 100 ( $100 \times \frac{(\text{observed score} - \text{min possible score})}{(\text{max possible score} - \text{min possible score})}$ ). The total score, resulting from the sum of the subscale scores, is also normalized to a 0–100 range. For C&A-GTS-QOL, if a response to 1 question is missing within the subscale, the missing response will be replaced with the average of the remaining responses within the subscale; if responses to 2 or more questions within a subscale are missing, the missing responses will not be replaced and the subscale score will be set to missing; if at least 1 subscale is missing then the total score will be set to missing. For all analysis and summary, transformed scores will be used.

8.1.5. [REDACTED]

[REDACTED]

[REDACTED]

8.1.6. [REDACTED]

[REDACTED]

[REDACTED]

This document is confidential.

## 8.2. Primary Efficacy Endpoint and Analysis

### 8.2.1. Primary Efficacy Analysis

The primary analysis will be a mixed-model, repeated-measures with the change in the TTS as the dependent variable. The model will include fixed effects for treatment group, week (3 levels: weeks 2, 4, and 8), and the treatment group by week interaction. The baseline TTS, region, and age group at baseline (2 levels: 6-11 year, 12-16 years) will be included as covariates. The unstructured covariance matrix for repeated observations within patients will be used. In case that the model does not converge, the Maximum-Likelihood estimation method will be used instead of the default Restricted Maximum-Likelihood. If the model still does not converge, then a simpler covariance structure with fewer parameters will be used, according to the following order: Heterogeneous Autoregressive (1), Heterogeneous Compound Symmetry, Autoregressive (1), and Compound Symmetry. The Kenward-Roger approximation will be used to estimate denominator degrees of freedom.

The least squares means of the change in TTS from baseline at week 8 will be compared (primary: TEV-50717 high-dose arm vs. the placebo arm; secondary: TEV-50717 low-dose arm vs. the placebo arm) using 2-sided tests at the alpha=0.05 level of significance. The SAS code for this test is as follows:

The least square (LS) mean and standard error for the treatment groups, and the LS mean difference, 95% confidence interval (CI), and p-value for each comparison (TEV-50717 high-dose vs. placebo at week 8; TEV-50717 low-dose vs. placebo at week 8) will be presented.

Cohen's d effect size will also be computed for each comparison (Kelley, 2007). Cohen's d is calculated as:

$$d = (\mu_t - \mu_p) / (\text{pooled SD}),$$

where  $\mu_t$  represents the least-square (LS) mean of the specified TEV-50717 group (High- or Low-dose),  $\mu_p$  is the LS mean of the placebo group, and the pooled SD is based on the adjusted LS means and adjusted standard errors from the mixed-effect model for MMRM, specifically:

$$\text{Pooled SD} = \frac{\text{Standard Error (SE)}}{\sqrt{\frac{1}{nt} + \frac{1}{np}}}$$

and nt=number of patients in specified TEV-50717 group and np=number of patients in placebo group.

The utility of Cohen's d is to help judge the clinical importance of a measured treatment difference.

### 8.2.2. Sensitivity Analysis

The primary efficacy analysis on change in the TTS at Week 8 is to use MMRM model, described in Section 8.2.1 (the primary analysis model), using all observed data in the mITT analysis set. Data from patients that had dose reduction, suspension, treatment discontinuation, or treatment-related adverse events were collected in the study and will be included in the analyses, as these patients are generally

This document is confidential.

**Statistical Analysis Plan for Interventional Studies**

Sponsor: Teva Branded Pharmaceutical Products R&D, Inc./Nuvelution TS Pharma, INC.;  
Protocol No.: TV50717-CNS-30060

---

not excluded from the mITT analysis set. This model is appropriate when data isMAR. This approach is considered reasonable under the assumption that the percent of early terminations will be low. As of 12 Dec 2019 the overall early termination rate from study 30060 was 8%, which is regarded to be in line with this assumption. Therefore, the proposed analysis is suitable for the primary estimand.

To assess the robustness of the primary efficacy analysis, the following additional analyses will include:

[REDACTED]

Details of sensitivity analysis for missing data and the statistical model are explained in the next 2 sections.

8.2.2.1. Sensitivity analyses for missing data

[REDACTED]

This document is confidential.

**Statistical Analysis Plan for Interventional Studies**

Sponsor: Teva Branded Pharmaceutical Products R&D, Inc./Nuvelution TS Pharma, INC.;

Protocol No.: TV50717-CNS-30060

---

[REDACTED]

[REDACTED]

[REDACTED]

[REDACTED]

[REDACTED]

[REDACTED]

[REDACTED]

[REDACTED]

[REDACTED]

[REDACTED]

[REDACTED]

[REDACTED]

[REDACTED]

[REDACTED]

[REDACTED]

[REDACTED]

[REDACTED]

[REDACTED]

[REDACTED]

[REDACTED]

[REDACTED]

[REDACTED]

[REDACTED]

[REDACTED]

This document is confidential.

[REDACTED]

The complete multiple imputation methodology, along with SAS code, is detailed in Appendix C (Section 19.3).

#### 8.2.2.2. Sensitivity analysis for the statistical model

#### 8.2.3. Subgroup Analysis

[REDACTED]

Data summary of TSS of YGTSS by subgroup below will be conducted using the mITT population. In addition, 95% CI for the change from baseline will be provided:

- Gender: Male and Female
- Race Group: White, Black or African American, and Other
- Baseline Age Group (6-11 years, 12-16 years)
- CYP2D6 impairment status (Yes/No)

In addition, TTS of YGTSS will be analyzed in the same fashion as the primary analysis in Section 8.2.1 by baseline age group, with the exception that age group will not be included as the fixed effect.

### 8.3. Secondary Efficacy Endpoint(s) and Analyses

The secondary endpoints for this study are as follows:

1. Change in the Tourette Syndrome-Clinical Global Impression (TS-CGI) score from baseline to week 8 between high-dose TEV-50717-treated patients and placebo-treated patients;
2. Change in the TTS of YGTSS from baseline to week 8 between low-dose TEV-50717-treated patients and placebo-treated patients;
3. Change in the TS-CGI score from baseline to week 8 between low-dose TEV-50717-treated patients and placebo-treated patients;
4. Change in the Tourette Syndrome-Patient Global Impression of Impact (TS-PGII) score from baseline to week 8 between high-dose TEV-50717-treated patients and placebo-treated patients;
5. Change in the Tourette Syndrome-Patient Global Impression of Impact (TS-PGII) score from baseline to week 8 between low-dose TEV-50717-treated patients and placebo-treated patients;
6. Change in the Child and Adolescent Gilles de la Tourette Syndrome – Quality of Life (C&A-GTS QOL) activities of daily living (ADL) subscale score from baseline to week 8 between high-dose TEV-50717-treated patients and placebo-treated patients;

This document is confidential.

7. Change in the C&A-GTS-QOL ADL subscale from baseline to week 8 between low-dose TEV-50717-treated patients and placebo-treated patients.

A hierarchical (fixed-sequence) testing approach will be used for the analysis of the primary and key secondary endpoints to maintain the experiment-wise type I error rate of 5%. If an endpoint is not statistically significant, confirmatory hypothesis testing will not be carried out on the remaining hypotheses, and remaining hypotheses will be considered exploratory rather than confirmatory.

Secondary efficacy analyses will be based on mITT analysis set.

8.3.1. Secondary Efficacy Analysis

8.3.1.1. Analysis of the change in the TS-CGI from baseline to Week 8

The change in the TS-CGI score from baseline to Week 8 (1st and 3rd secondary endpoints) will be analyzed in the same fashion as the primary analysis in Section 8.2.1, with the exception that the baseline value of the given endpoint will be included as the covariate.

8.3.1.2. Analysis of the change in the TTS of YGTSS between low-dose TEV-50717-treated patients and placebo-treated patients

The change in the TTS of YGTSS from baseline to Week 8 between low-dose TEV-50717 treated patients and placebo-treated patients (2nd secondary endpoint) will be analyzed as part of Section 8.2.1.

8.3.1.3. Analysis of the change in TS-PGII

The change in the TS-PGII score from baseline to Week 8 (4th and 5th secondary endpoints) will be analyzed using a Cochran-Mantel-Haenszel (CMH) row mean score test with modified ridit scoring, controlling for baseline TS-PGII. The TS-PGII will be summarized as shifts from baseline score to each visit that it is measured using descriptive statistics.

The SAS code for the analysis at week 8 for each pair of high-dose TEV-50717 and placebo, or low-dose TEV-50717 and placebo is as follows:

[REDACTED]

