Analysis of Primary Endpoint: The primary efficacy endpoint for this study is the change in the TTS of the YGTSS from baseline to week 8 between high-dose TEV-50717-treated and placebo-treated patients. The primary analysis will be a mixed-model repeated-measures model with the change in the TTS as the dependent variable. The model will include fixed effects for treatment group, week (3 levels: weeks 2, 4, and 8), and the treatment group-by-week interaction. The baseline TTS, region, and age group at baseline (2 levels: 6 to 11 years, 12 to 16 years) will be included as covariates. The unstructured covariance matrix for repeated observations within patients will be used. The least squares means of the change in TTS from baseline at week 8 will be compared between the high-dose treatment arm and the placebo arm using a 2-sided test at the $\alpha = 0.05$ level of significance. In addition, actual values and changes in the TTS from baseline to each visit will be summarized using descriptive statistics.

Analysis of Key Secondary Endpoints: A hierarchical (fixed-sequence) testing approach will be used for the analysis of the key secondary endpoints. If an endpoint is not statistically significant, confirmatory hypothesis testing will not be carried out on the remaining hypotheses, and remaining hypotheses will be considered exploratory rather than confirmatory. The following analyses of key secondary endpoints will be conducted:

1. The change from baseline to week 8 in TS-CGI will be analyzed using a similar model as the primary analysis; however, instead of change in YGTSS TTS as the dependent variable and baseline YGTSS TTS as a covariate, the corresponding TS-CGI values will be used. The comparison between high-dose TEV-50717 and placebo will be tested.
2. Using the same model as for the primary analysis, the comparison between the change in the TTS of the YGTSS from baseline to week 8 for low-dose TEV-50717 and placebo will be tested.
3. Using the same model as described in endpoint #1 above for TS-CGI, the comparison between the change in the TS-CGI values from baseline to week 8 for low-dose TEV-50717 and placebo will be tested.
4. The change from baseline to week 8 in TS-PGII will be analyzed using a Cochran-Mantel-Haenszel row mean score test with modified ridit scoring controlling for age group. The comparison between high-dose TEV-50717 and placebo will be tested.

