9. STATISTICS

This section describes the statistical analysis as foreseen at the time of planning the study. Changes, additions, and further details about the analyses will be described in the statistical analysis plan. After finalization of the statistical analysis plan, any additional analyses or changes to analyses that may be required will be fully disclosed in the CSR.

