9.5.5.3. Key Secondary Efficacy Analyses

A hierarchical (fixed-sequence) testing approach will be used for the analysis of the key secondary endpoints. If an endpoint is not statistically significant, confirmatory hypothesis testing will not be carried out on the remaining hypotheses, and remaining hypotheses will be considered exploratory rather than confirmatory. The following analyses of key secondary endpoints will be conducted:

1. The change from baseline to week 8 in TS-CGI will be analyzed using a similar model as the primary analysis; however, instead of change in YGTSS TTS as the dependent variable and baseline YGTSS TTS as a covariate, the corresponding TS-CGI values will be used. The comparison between high-dose TEV-50717 and placebo will be tested.
2. Using the same model as for the primary analysis, the comparison between the change in the TTS of the YGTSS from baseline to week 8 for low-dose TEV-50717 and placebo will be tested.
3. Using the same model as described in endpoint #1 above for TS-CGI, the comparison between the change in the TS-CGI values from baseline to week 8 for low-dose TEV-50717 and placebo will be tested.
4. The change from baseline to week 8 in TS-PGII will be analyzed using a Cochran-Mantel-Haenszel-row mean score test with modified ridit scoring controlling for age group. The comparison between high-dose TEV-50717 and placebo will be tested.
5. Using the same model as described in endpoint #4 above for TS-PGII, the comparison between the change in the TS-PGII values from baseline to week 8 for low-dose TEV-50717 and placebo will be tested.
6. The change from baseline to week 8 in the C&A-GTS-QOL ADL subscale will be analyzed using a similar model as the primary analysis; however, instead of change in YGTSS TTS as the dependent variable and baseline YGTSS TTS as a covariate, the

corresponding C&A-GTS-QOL ADL subscale values will be used. The comparison between high-dose TEV-50717 and placebo will be tested.

7. Using the same model as described in endpoint #6 above for the C&A-GTS-QOL ADL subscale, the comparison between the change in the C&A-GTS-QOL ADL subscale scores from baseline to week 8 for low-dose TEV-50717 and placebo will be tested.

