9.11. Reporting Deviations from the Statistical Plan

Deviations from the statistical plan, along with the reasons for the deviations, will be described in protocol amendments, the statistical analysis plan, the CSR, or any combination of these, as appropriate, and in accordance with applicable national, local, and regional requirements and regulations.

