#### **3.2. Secondary Estimands**

The secondary estimands are:

- (1) the difference in means between TEV-50717 high dose and placebo for the change in the Tourette Syndrome - Clinical Global Impression (TS-CGI) score from baseline to week 8;
- (2) the difference in means between TEV-50717 low dose and placebo for the change in the TTS of the YGTSS from baseline to week 8;
- (3) the difference in means between TEV-50717 low dose and placebo for the change in the TS-GCI score from baseline to week 8;
- (4) the difference in means between TEV-50717 high dose and placebo for the change in the Tourette Syndrome - Patient Global Impression of Impact (TS-PGII) score from baseline to week 8;
- (5) the difference in means between TEV-50717 low dose and placebo for the change in the TS-PGII score from baseline to week 8;
- (6) the difference in means between TEV-50717 high dose and placebo for the change in the Child and Adolescent Gilles de la Tourette Syndrome - Quality of Life (C&A-GTS-QOL) activities of daily living (ADL) subscale score from baseline to week 8;
- (7) the difference in means between TEV-50717 low dose and placebo for the change in the C&A-GTS-QOL ADL subscale score from baseline to week 8,

in the target patient population of children and adolescents with TS who receive at least 1 dose of IMP and have both a baseline and at least 1 post-baseline YGTSS assessment, regardless of whether or not dose reduction, suspension, or treatment discontinuation occurred, and regardless of treatment-related adverse events. For the intercurrent event of study discontinuation, all data collected until time of study discontinuation will be included and a missing at random (MAR) assumption will be hypothesized.

The secondary estimands assess the effectiveness of TEV-50717 high dose and TEV-50717 low dose in the reduction of motor and phonic tics associated with TS and the impact of the reduction in tics on the patients' quality of life as assessed by the clinicians and the patients, focusing on the causal effects attributable to the investigational medicinal product (IMP).

This document is confidential.

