## **12. Changes from Analysis Planned in Protocol**

A new exploratory endpoint is added:

■ [REDACTED]

This document is confidential.

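### SAP 3.2 defines the TS-PGII estimands as differences in means, but the visible main analysis is a rank-type test with no planned mean difference or CI; its changed control factor is also not listed in section 12

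*SAP*

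**What the plan says.** **Estimand.** SAP 3.2 was added in SAP version 2.0. Item 5 is "the difference in means between TEV-50717 low dose and placebo for the change in the TS-PGII score from baseline to week 8"; item 4 is the same for the high dose. As for all secondary estimands, study discontinuation is handled by including the data collected up to that point and assuming MAR.

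**Main analysis.** SAP 8.3.1.3 specifies, for both doses at week 8, a CMH "row mean score test with modified ridit scoring, controlling for baseline TS-PGII". It adds descriptive shifts from baseline to each visit. The SAS code is blacked out in the public copy.

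**The other key secondaries.** SAP 8.3.1.1, 8.3.1.2 and 8.3.1.4 send TS-CGI, low-dose TTS and the ADL subscale to the model in 8.2.1, whose stated output includes the LS-mean difference, its 95% CI and a p-value.

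**Protocol.** Section 9.5.5.3, item 4, has the same test but as a "row mean score test with modified ridit scoring controlling for age group". The synopsis agrees, and item 5 uses the same method for the low dose. Age group is the stratification factor in Protocol 5.9.

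**Who may change what.** Protocol section 9 says: "Changes, additions, and further details about the analyses will be described in the statistical analysis plan". Protocol 9.11 says that deviations and their reasons "will be described in protocol amendments, the statistical analysis plan, the CSR, or any combination of these, as appropriate". The visible text of SAP section 12 says only "A new exploratory endpoint is added".

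**Position in the sequence.** TS-PGII occupies steps 5 and 6 of the fixed sequence, before the two ADL tests. SAP 8.3 states: "If an endpoint is not statistically significant, confirmatory hypothesis testing will not be carried out on the remaining hypotheses".

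**The concern.** An estimand names a quantity to be estimated. For TS-PGII that quantity is a difference in means, but the analysis planned for it produces a test and not that difference. If the sequence reaches TS-PGII and the test succeeds, the report would claim an effect on a patient-rated scale without a pre-planned estimate of its size or precision on the scale that the SAP itself chose.

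The second matter is traceability. A reader comparing the two documents finds different control factors for a confirmatory test, and from the visible text cannot tell a deliberate choice from a drafting slip.

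**Working it through.** **1. The plan's own figures.** Neither document gives an effect, distribution or power for TS-PGII. The only design figure concerns TTS and it reproduces: n per arm = 2 × (1.960 + 1.282)² × (9.5/6.5)² = 2 × 10.51 × 2.136 = 44.9, so 45; allowing 10% dropout, 45/0.90 = 50. It does not bear on this point.

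**2. What the CMH test returns.** In stratum h, with n_h patients of whom n_1h are on active drug, each patient gets r = rank/(n_h + 1). The statistic is

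Q = [Σ_h (sum of r on active − n_1h × mean r_h)]² / Σ_h V_h,

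V_h = n_1h (n_h − n_1h) / [n_h (n_h − 1)] × Σ (r − mean r_h)²,

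referred to chi-square with 1 df. With baseline TS-PGII as the stratum, change equals the week-8 score minus a constant, so ranking change is the same as ranking the week-8 score. In 800 simulated trials the two p-values were equal every time. Respacing the five answers unevenly while keeping their order leaves every rank, Q and the p-value unchanged, but alters the mean difference. The mean difference therefore cannot be recovered from the test.

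**3. Estimand against analysis.**

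| Key secondary | Estimand (3.2) | Visible main analysis | Planned estimate |
|---|---|---|---|
| 1, 3 TS-CGI | difference in means | 8.2.1 MMRM | LS-mean difference, 95% CI |
| 2 TTS, low dose | difference in means | 8.2.1 MMRM | LS-mean difference, 95% CI |
| 4, 5 TS-PGII | difference in means | week-8 CMH, descriptive shifts | none visible |
| 6, 7 ADL | difference in means | 8.2.1 MMRM | LS-mean difference, 95% CI |

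**4. Use of incomplete patients.** TS-PGII is collected at weeks 2, 4 and 8. The week-8 test does not use the week 2 and 4 scores of a patient without a week-8 value. At the 8% early termination rate in SAP 8.2.2, that is at most 0.08 × 150 = 12 patients, 4 per arm. Fewer are affected if the redacted visit windows map early termination visits to week 8.

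To size the bias, trials were simulated under assumed inputs:
- 50 per arm;
- five categories cut from a normal latent score at −1.8, −0.8, 0.2 and 1.2;
- a latent shift of 0.5 or 0.65 SD;
- dropout after week 4, either completely at random or depending on the week-4 score, including in opposite directions by arm;
- 1,500 trials per setting.

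| Missing at week 8 | Bias, week-8-only mean difference | Bias, MMRM-type estimate |
|---|---|---|
| 8% | −0.033 to +0.030 | within 0.004 |
| 15% (SAP 7.1 trigger) | −0.073 to +0.062 | within 0.006 |

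At 8% missing, the simulated SD of the estimates was 0.156 to 0.204, so the 95% CI half-width would be 1.96 × 0.156 = 0.31 to 1.96 × 0.204 = 0.40 points.

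**5. The control factor.** Stratifying by baseline compares week-8 scores among patients who started equal. Stratifying by age group ranks raw change across all starting levels within an age group. These are different tests, but each holds its level. With no effect, rejection was 4.5% to 5.4% (age group) and 4.7% to 5.1% (baseline) over four settings of 4,000 trials. A separate set with 3,000 runs per setting gave 4.5% to 6.0%, with a simulation SE of √(0.05 × 0.95/3000) = 0.4 points.

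As illustration only: with an assumed 0.5 SD effect and baseline-to-week-8 correlations of 0.3, 0.5 and 0.7, the two versions fell on different sides of 0.05 in 27%, 19% and 13% of trials.

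**The case against.** **Precedence is settled.** The protocol lets the SAP change analyses. The SAP post-dates Protocol Amendment 03 and states its control factor openly, and the reason may still appear in the CSR. This stands. A reader might infer that the confirmatory test is left undecided between two documents; the documents do not support that. Only the missing section 12 entry and reason remain.

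**Redaction.** The SAS code in 8.3.1.3, the text of 8.3.2 and the body of Appendix D are blacked out. Age group may be a second stratum in the code, so it cannot be said that the SAP drops it. The visible title of Appendix D refers to combining CMH statistics over imputations, so missing TS-PGII data may well be handled in sensitivity analyses. This also stands. But the sentence defining the main analysis is visible, and adding a stratum to a rank-type test does not turn it into an estimate of a mean difference.

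**The shift summary carries information.** If the shifts are tabulated as counts by arm, a reader could work out each arm's raw mean change and an unadjusted difference. That is fair, so it would be too strong to say that no effect information will exist. Such a figure would still be unadjusted, derived after the fact, and blind to the earlier scores of patients who left, so it is not the MAR estimate that 3.2 describes.

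**A rank-type test suits a 5-point item.** Agreed, and both documents choose one. That is a reason to keep the test and to make 3.2 and 8.3.1.3 agree. It does not make them agree.

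**Conclusion.** The point holds, at minor to moderate weight. Its main part is that estimands 4 and 5 are differences in means with no planned mean difference or CI in the visible main analysis, alone among the key secondaries. This follows from the visible text and needs no assumption. The lesser part is an unlisted and unexplained change of control factor, which is a documentation gap.

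Two stronger readings are not supported. A reader might infer inflated type I error: either test holds 5% when it is the one pre-specified, and the SAP pre-specifies one. A reader might infer serious missing-data bias: at 8% missing it is about 0.03 points at most, and about 0.07 at 15%. Those sizes rest wholly on the assumed TS-PGII distribution, effect and dropout pattern.

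The disagreement rates between the two control factors are illustrative, not a forecast for this trial. They would matter only if someone ran the protocol version beside the SAP version, and only if the primary and key secondaries 1 to 3 had already succeeded.

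**What to change.** In the SAP, before unblinding:

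1. Keep the CMH test as the confirmatory test. In 8.3.1.3, add the week-8 LS-mean difference with 95% CI for each dose against placebo from the 8.2.1 MMRM, with baseline TS-PGII as covariate and weeks 2, 4 and 8 as the repeated visits. Label it the supporting estimate for estimands 4 and 5, with no role in the testing sequence. Alternatively, restate the summary measure of these two estimands in 3.2 to match the rank-based test, and say there how patients without a week-8 score are handled.
2. As a minor correction, list the change from age group to baseline TS-PGII in section 12 with its reason, and state in 8.3.1.3 whether age group is also a stratum.

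The cost is one or two sentences in 8.3.1.3 (or 3.2), one entry in section 12 and one more run of an existing model. No new data are needed, and Protocol section 9 makes a protocol amendment unnecessary. The downside of the supporting estimate is that it treats a 5-point item as continuous and could differ in tone from the CMH result, which is why its supporting role should be stated. If the unredacted SAP already contains these items, nothing further is needed.
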